# Study visits for randomized subjects

**Screening Visit:** A screening visit will take place to determine eligibility for enrollment. Participants will be asked to complete the MGH ATRQ and sign release of information forms to request documentation from prescribing clinicians. It is estimated that after review of detailed source documents describing past treatment details, 60 women will be confirmed to have partial/nonresponse to antidepressant therapy and be eligible for the randomized, placebo-controlled phase. Screening visit testing will include:

- o complete medical history
- o physical examination, including height and weight
- 0800h Blood draw for ALT, creatinine, CBC, thyroid stimulating hormone (TSH), free testosterone, FSH, urine pregnancy and toxicology
- o diagnostic interview with SCID
- MDD symptom assessment with MADRS
- completion of the MGH ATRQ

If antidepressant-resistance is confirmed following screening procedures, the subject will be scheduled for a baseline visit approximately 1-2 weeks.

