# Baseline Visit for the Randomized, Placebo-Controlled, Augmentation Study: Eligible

subjects will undergo baseline testing immediately before the augmentation phase of the protocol. Baseline visit testing will include the following. However, the blood draw will not be repeated if the Baseline visit occurs within 2 weeks of the screening visit.

- Weight, vital signs, waist-to-hip ratio, and consumptive habits (alcohol, caffeinated beverages) will be recorded
- Urine pregnancy test (for premenopausal women only). Postmenopausal is defined as at least one year since last menses and FSH in the postmenopausal range
- Baseline endocrine blood testing: free testosterone, estradiol, neuroactive steroid panel, DHEAS, blood cortisol, late night salivary cortisol and 8 a.m. salivary cortisol
- o Baseline safety blood testing: ALT, creatinine, CBC
- Depression: MADRS, IDS-SR, CGI-I, S
- Cognitive Functioning: CPFQ
- o Persistent/residual symptom assessment: SF-36, BFI, ESS, FSS, DISF
- Safety assessments: SAFTEE-SI, CHRT, and hirsutism and skin assessments
- We will distribute the Study Drug Compliance and Hot Flash Diary or Menopausal Symptom Diary

• We will also collect DNA to be banked for a future exploratory study into whether androgen receptor CAG repeat length moderates androgen-behavior relationships (based on data by Seidmanet *et al.*).

**Follow-up Visits (Placebo-Controlled Augmentation Phase):** Subjects will then be randomized to receive low-dose testosterone or placebo. Follow-up visits will take place at weeks 2, 4, 6 and 8 post-baseline. Follow up visits will include:

- Urine pregnancy test (for premenopausal women only). Postmenopausal is defined as at least one year since last menses and FSH in the postmenopausal range (weeks 2, 4, 6 and 8)
- Free testosterone levels (weeks 2, 4, 6 and 8)
- Skin evaluations to monitor for side effects (weeks 4 and 8)
- Weight and vital signs will be recorded (weeks 4 and 8)
- Waist-to-hip ratio (week 8)
- Depression: MADRS, IDS-SR, CGI-I, S (weeks 2, 4, 6 and 8)
- Cognitive Functioning: CPFQ (weeks 2, 4, 6 and 8)
- Persistent/residual symptom assessment: SF-36, BFI, ESS, FSS, DISF (weeks 2, 4, 6 and 8)
- Safety: SAFTEE-SI, CHRT (weeks 2, 4, 6 and 8)
- Estradiol levels (weeks 2, 4, 6 and 8)
- Salivary cortisol (week 8)
- Medication management sessions (weeks 2, 4, 6 and 8)
- Neuroactive steroid panel (week 8)

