Specific Aim 2: We will investigate in women with partial/nonresponse to antidepressant therapy whether adjunctive low-dose testosterone is safe and welltolerated in women with partial/nonresponse to antidepressant therapy. Experimental Strategy and Endpoints: To investigate whether adjunctive physiologic testosterone is safe and well-tolerated over the 8-week protocol, we will compare rates of adverse events in subjects randomized to testosterone augmentation to those receiving placebo using the SAFTEE-SI. These endpoints will also include increases in ALT and hirsutism and skin assessment scores and decreases in HDL cholesterol. The primary endpoint will be adverse effect rate.

• These data will determine whether adjunctive physiologic testosterone is safe and well-tolerated in women with relative partial/nonresponse to antidepressant therapy.

Data Analysis: Rates for each adverse effect will be computed by group. Differences between treatment groups in dropout rates will be examined using a Fisher's Exact test, though every effort will be made to retain subjects through the 8-week course. If a trend (p < .10) indicative of differential dropout is detected, a more detailed survival analysis will be completed to illustrate the timing and magnitude of these differences.

Specific Aim 3: Low-dose testosterone augmentation improves persistent/residual symptoms in women with antidepressant-resistant depression.

Experimental Strategy and Endpoints: To investigate the effects of low-dose testosterone augmentation on fatigue and energy in women with antidepressant-resistant depression, the 50 women with antidepressant-resistant depression

randomized to testosterone augmentation and 50 to the placebo arm of the 8-week randomized, double-blind placebo controlled study delineated in the "Overall Protocol", will be compared. Energy/fatigue and sexual function/libido endpoints will be measured at baseline and weeks 2, 4, 6 and 8. The primary endpoint will be BFI score weeks 2-8.

• These data will determine the effects of low-dose testosterone augmentation on fatigue and sexual function in women with antidepressant-resistant depression.

Data Analysis: The data will be analyzed using a mixed-effect linear regression model, using methods and assumptions as in Specific Aim 1 Data Analysis, above.

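### SAP Aim 2 names ALT increases and HDL decreases as safety endpoints, but the supplied protocol schedules no on-treatment ALT and no HDL at any visit

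*SAP*

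**What the plan says.** The SAP, under Specific Aim 2, compares adverse events between arms over 8 weeks using the SAFTEE-SI and then adds: "These endpoints will also include increases in ALT and hirsutism and skin assessment scores and decreases in HDL cholesterol". It states that "The primary endpoint will be adverse effect rate", so ALT and HDL are additional endpoints. The analysis text says "Rates for each adverse effect will be computed by group" and gives no separate method for laboratory values. The conclusion it expects is broad: "These data will determine whether adjunctive physiologic testosterone is safe and well-tolerated".

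The protocol's visit lists for randomized women contain the following.

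- **Screening:** "0800h Blood draw for ALT, creatinine, CBC, thyroid stimulating hormone (TSH), free testosterone, FSH, urine pregnancy and toxicology". After that, "the subject will be scheduled for a baseline visit approximately 1-2 weeks".
- **Baseline:** "Baseline safety blood testing: ALT, creatinine, CBC", with the proviso that "the blood draw will not be repeated if the Baseline visit occurs within 2 weeks of the screening visit".
- **Weeks 2, 4, 6 and 8:** the laboratory items are a urine pregnancy test (premenopausal women), free testosterone and estradiol at all four visits, and salivary cortisol and the neuroactive steroid panel at week 8. The items labelled as safety are the SAFTEE-SI and CHRT at all four visits; skin evaluations are at weeks 4 and 8.

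The blood taken on fMRI days is for hormone levels. The protocol's Safety paragraph mentions routine laboratory tests only as a step before the randomized phase.

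**The concern.** An ALT increase on treatment cannot be seen without an ALT taken on treatment, and an HDL decrease cannot be seen without an HDL. The SAP names both, and the supplied schedule provides for neither. A safety conclusion that appears to cover liver enzymes and lipids would then have no data behind that part of it. Safety is one of the trial's specific aims, and the SAP itself chose these two markers. The SAFTEE-SI is not a laboratory assay and cannot supply the values. Clinically apparent events can still be reported, but a laboratory change without symptoms would not be seen.

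**Working it through.** The documents give no figure to reproduce; the check is a count. The inputs are the protocol's Screening, Baseline, Follow-up and fMRI substudy visit lists for randomized women: 6 visits (screening, baseline, weeks 2, 4, 6, 8), of which 4 are on treatment.

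| Item | Screening | Baseline | Weeks 2, 4, 6, 8 | Total |
|---|---|---|---|---|
| ALT, baseline within 2 weeks of screening | 1 | 0 | 0 of 4 | 1 of 6 |
| ALT, baseline later than 2 weeks | 1 | 1 | 0 of 4 | 2 of 6 |
| HDL or any lipid | 0 | 0 | 0 of 4 | 0 of 6 |

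For comparison, the SAFTEE-SI, free testosterone and estradiol are each listed at 4 of 4 follow-up visits.

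1. **ALT before treatment.** The planned gap is about 1 to 2 weeks and the draw is not repeated inside 2 weeks, so a single ALT is the expected case.
2. **ALT on treatment.** 100 women × 0 scheduled values = 0 values. Neither a change from baseline nor a rate of abnormal values can be formed.
3. **HDL.** 100 women × 0 scheduled values = 0 values, before or during treatment. In the two documents HDL appears only in the SAP's endpoint sentence.
4. **Other possible sources.** The fMRI-day draws are for hormones. For the Data Safety Monitor's review, the protocol names adverse events and free testosterone, not ALT or lipids.
5. **Analysis rule.** If the laboratory changes are meant to count among the adverse effect rates, a cutoff is needed for an ALT increase and an HDL decrease. Aim 2 gives none. A continuous comparison would need no cutoff, but Aim 2 does not specify one either.

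**The case against.** The strongest reply is that a short visit list is weak evidence that a test was not planned. The protocol is an institutional application form that asks for a brief description of procedures, and the SAP refers to an overall protocol that may be a separate, fuller document. The lists do omit other planned items. The Beck Suicide Index is to be used at each visit but is in no visit list. DHEAS and blood cortisol, whose 8-week changes the SAP's Aim 1 secondary analyses use, are not in the follow-up list. This stands as a limit: the documents do not show that samples were never taken. It does not remove the mismatch. The follow-up list assigns weeks item by item, down to the waist-to-hip ratio, and includes no safety blood test.

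A second reply is that the protocol (5/19/2017) is later than the SAP (February 1, 2017), so the endpoint sentence may be leftover text. That is possible and would favour deletion, but the SAP still needs correcting.

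Third, the rule on not repeating blood may cover only the tests common to both visits, because baseline adds hormones not drawn at screening. ALT is common to both, so its count does not change. On that reading a baseline sample is still taken, and HDL could be added to it.

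Finally, these are not primary endpoints. That is correct and limits the severity.

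**Conclusion.** The concern holds. As scheduled in the supplied protocol, ALT is measured at 0 of 4 follow-up visits and HDL at 0 of 6 visits, so two endpoints named in SAP Aim 2 cannot be computed for any of the 50 + 50 randomized women. This rests on the visit lists being the operative schedule; if a fuller document contains the tests, the defect is only a missing reference. The demonstrated effect is confined to these two endpoints and to the part of the safety conclusion that depends on them. The adverse effect rate and the MADRS analysis are untouched. It should be fixed but does not threaten the main result.

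**What to change.** Reconcile the SAP and the protocol in one of two ways.

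**(a) Keep the endpoints.** Add ALT and HDL assays to the week-8 blood already drawn, and HDL to whichever pre-treatment sample is actually taken, where that is still possible. State the comparison in Aim 2: for example, the week-8 value by arm adjusted for the pre-treatment value, with a 95% confidence interval. If rates are to be reported, state the cutoff for each change. Where no pre-treatment HDL exists, an unadjusted comparison of the arms at week 8 remains valid but is less precise. Cost: 2 × 100 = 200 week-8 assays plus 0 to 100 pre-treatment HDL assays, so 200 to 300 in all, and a short amendment. No extra visit is needed. The count assumes that all 100 women reach week 8 and that none had already passed it; the documents give no accrual status.

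**(b) Drop the endpoints.** Delete ALT and HDL from Aim 2 and state that the safety conclusion does not cover liver enzyme or lipid changes. This is a text change only, at the price of a narrower conclusion.

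If a fuller protocol already schedules the tests, cite that schedule in the SAP. In the same check, confirm on-treatment DHEAS and blood cortisol for the Aim 1 secondary analyses. Confirm also when hirsutism is scored on treatment: the follow-up list names only skin evaluations, and the Safety paragraph mentions hirsutism assessment without a time point.

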#### **RESEARCH DESIGN AND METHODS**

Briefly describe study design and anticipated enrollment, i.e., number of subjects to be enrolled by researchers study-wide and by Partners researchers. Provide a brief summary of the eligibility criteria (for example, age range, gender, medical condition). Include any local site restrictions, for example, "Enrollment at Partners will be limited to adults although the sponsor's protocol is open to both children and adults."

**Study Design:** After antidepressant therapy partial or nonresponse is established by documentation of failure to at least 8 weeks' treatment with an adequately dosed antidepressant therapy, A minimum of 100 subjects study-wide (60 from MGH) with MADRS $\geq$ 12 will enter the double-blind augmentation randomized-placebo-controlled treatment study. 50 of these subjects will be on active study drug and 50 will be control subjects on placebo. Eligible subjects will undergo baseline assessment of symptoms and biological measures and then be randomized to 1 of 2 groups: low-dose physiologic testosterone augmentation by transdermal preparation or placebo.

Antidepressant dose will be held steady during the trial. Outcome measures will examine the antidepressant efficacy of physiologic testosterone treatment (Aim 1), its tolerability (Aim 2) and its effects on 2 specific RDoC symptoms (Aim 3).

**Subject Enrollment:** A total of 330 women will be enrolled study-wide, of which 100 women with antidepressant-resistant MDD and 50 women with no psychiatric history will be eligible study-wide. Study subjects for the depressed population will be women, ages 21-75 with failure to remit following at least 8 weeks antidepressant trial documented by past treatment history.

In addition, 20 healthy controls without

depression will be recruited for the fMRI substudy healthy control population.

Up to 60 postmenopausal women who do not have current or past psychiatric disorders will also be screened to obtain 30 women who will be enrolled

as healthy controls.

Randomized Study Subject Population (n=60)

Inclusion Criteria for Randomized Study Subjects:

- 1. Female, age 21-75, who provide written informed consent
- 2. Free testosterone level no higher than the third quartile of the normal range
- 3. Meet DSM-IV criteria (by SCID) for current Major Depressive Disorder and have MADRS≥12

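### Aim 2 reports adverse effects as per-group rates with no between-arm difference or interval and no stated use of the baseline SAFTEE-SI, and looks at drop-out timing only if Fisher p<.10

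*SAP*

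**What the plan says.** SAP, Specific Aim 2, sets the endpoint: "The primary endpoint will be adverse effect rate". It states an intention to compare with placebo: "we will compare rates of adverse events in subjects randomized to testosterone augmentation to those receiving placebo using the SAFTEE-SI". It also names ALT, hirsutism and skin scores, and HDL cholesterol as endpoints, each described as a rise or a fall.

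The Data Analysis paragraph that follows has two parts. On adverse effects it says "Rates for each adverse effect will be computed by group". On drop-out it plans a Fisher exact test between arms, with a survival analysis of timing and size added under a condition: "If a trend (p < .10) indicative of differential dropout is detected". The same section says of the result: "These data will determine whether adjunctive physiologic testosterone is safe and well-tolerated".

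The protocol's baseline visit lists "Safety assessments: SAFTEE-SI, CHRT, and hirsutism and skin assessments", and its follow-up schedule repeats the SAFTEE-SI at weeks 2, 4, 6 and 8. On size, the protocol says "50 of these subjects will be on active study drug and 50 will be control subjects on placebo".

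**The concern.** A rate in each arm does not answer a comparative safety question. The reader needs the difference and its precision, and the SAP specifies neither for its own primary safety endpoint. By contrast, Aim 1 has a specified model, and remission has a named test.

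The participants have current major depression and have taken an antidepressant for at least eight weeks. The protocol's Specific Aims section itself describes fatigue and reduced libido as common in this disorder. Many women may therefore endorse SAFTEE-SI items before the first dose. Unless an item must be new or worse to count, those women add equally to both arms and hide part of any excess on testosterone.

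The drop-out rule makes the display of timing depend on a significance test that is weak at this sample size. A tolerability difference of practical interest could occur without its timing being shown. The protocol intends a positive result to lead to a larger trial, so a safety statement firmer than the data allow would be carried forward.

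**Working it through.** The documents give no power, margin or detectable difference for Aim 2, so there is no planned figure to reproduce. They give no adverse-effect or drop-out rates by arm either. The rates below are assumptions, shown as ranges. The only input from the documents is 50 per arm.

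**1. Dilution if baseline complaints count.** Let p0 be the share of women with a complaint at baseline. Assume it persists in both arms and that worsening is not counted separately. Let q be new onset among the rest. The observed rate in an arm is p0 + (1 − p0)q, so the observed difference is (1 − p0)(qT − qP). With qT = 20% and qP = 10%:

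| p0 | Placebo | Testosterone | Difference |
|---|---|---|---|
| 0% | 10% | 20% | 10 points |
| 30% | 37% | 44% | 7 points |
| 50% | 55% | 60% | 5 points |
| 70% | 73% | 76% | 3 points |

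With a larger assumed effect, 30% versus 10% new onset, the power of a two-sided Fisher test at .05 falls from 64% with no baseline complaints to 24%, 13% and 7% at p0 of 30%, 50% and 70%.

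**2. Precision of a between-arm difference at 50 per arm.**
- At 20% in each arm, the 95% half-width is 1.96 × √(2 × 0.20 × 0.80 / 50) = 0.157, about ±16 points.
- Observed 10/50 versus 5/50: Newcombe 95% CI −4.3 to +24.2 points.
- Observed 5/50 versus 5/50: −12.7 to +12.7 points.
- No events in 50: the upper limit is 1 − 0.05^(1/50) = 5.8% one-sided, or 1 − 0.025^(1/50) = 7.1% two-sided.

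**3. How often the drop-out trigger fires.** The SAP does not state sidedness, so a two-sided test is assumed. The probability of firing is the sum of Bin(x; 50, pT) × Bin(y; 50, pP) over all pairs of counts (x, y) with Fisher p<.10.

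| Assumed drop-out, placebo v testosterone | Trigger fires |
|---|---|
| 2% v 10% | 32% |
| 0% v 10% | 57% |
| 5% v 15% | 39% |
| 10% v 20% | 31% |
| 5% v 20% | 66% |
| 10% v 25% | 54% |
| 10% v 30% | 75% |

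The smallest imbalances that fire it are 0 v 5, 1 v 7, 2 v 8 and 3 v 10 drop-outs. A result of 2 v 7 does not (p = 0.16).

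**4. Why power is low.** The .10 level is more lenient than .05, so it is not the cause. With equal true drop-out of 5%, 10% or 20%, the test rejects in only 2.2%, 4.9% and 5.8% of trials, not 10%. The cause is Fisher's conservatism together with 50 per arm.

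**The case against.** Four points on the other side are sound and limit the concern.

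- **Silence is not a rule.** A reader might infer that the SAP counts pre-existing complaints as adverse effects. It does not say so. It speaks of adverse effects, it frames the laboratory and skin endpoints as change, and the data for a new-or-worse count are collected. The dilution is conditional on a reading that the text leaves open.
- **A placebo comparison is planned.** What is missing is its estimate and interval. The aim also covers more than complaints.
- **The p<.10 rule is narrow.** It gates only the added survival analysis. The adverse-effect rates and the Fisher comparison of drop-out are done in any case. A reader might infer that a non-significant screen will be taken as no difference, but nothing in the SAP says that.
- **Aim 1's missing-data assumption is examined.** A reader might infer that the gate leaves missing-at-random unchecked. The Aim 1 analysis states the assumption, plans to seek 8-week observations on drop-outs too, and commits to a sensitivity analysis that does not depend on the trigger.

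It is also fair that descriptive safety reporting is usual in a trial of this size, that the wording about determining an answer recurs under Aims 1 and 3, and that the protocol leaves definitive proof to a later trial. The interval widths follow from the sample size, and no change of analysis narrows them.

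Two things remain. If the analysis is descriptive, the stated conclusion should match it. And because precision is poor, the difference and its interval need to be shown. The twice-yearly review by a Data Safety Monitor is trial oversight and does not supply the Aim 2 analysis.

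**Conclusion.** The point holds as a cheap improvement to the Aim 2 analysis. The SAP specifies no between-arm estimate or interval for its primary safety endpoint, and it leaves the use of baseline SAFTEE-SI scores open. Its drop-out trigger misses 61% of 5% versus 15% differences and 69% of 10% versus 20% differences. It fires more often than not in the 15- and 20-point cases above, and also for 0% versus 10%, so the weakness depends on the true rates.

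The dilution to 7 to 3 points rests on assumed onset and prevalence, on persistence of baseline complaints, and on those complaints being counted. The trigger figures rest on assumed drop-out rates, a two-sided test and 50 per arm. The precision figures rest on 50 per arm and, for the ±16 points, on a 20% rate.

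The documents do not support going further and saying that the plan will miss harm or is built to conclude that treatment is safe.

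**What to change.** In SAP, Specific Aim 2:

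1. Count a SAFTEE-SI item as an adverse effect when it is new or worse than that woman's own baseline at any of weeks 2 to 8.
2. Report the testosterone-minus-placebo risk difference with a 95% CI, for any such effect and for each item, alongside the rates by group.
3. Remove the p<.10 trigger. Always show time to drop-out by arm, with the difference and its 95% CI.
4. Replace the sentence that the data will determine safety with a statement of which excess risks the intervals do and do not exclude. As a guide, a 20% rate gives about ±16 points, and 0 of 50 still allows 5.8% (one-sided) or 7.1% (two-sided).

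This needs no new patients, visits or measurements. The cost is SAP wording, a little more analysis, and a more cautious safety statement. It does not raise power. It shows how much the trial can say.
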